## 1. Protocol Summary

### 1.1 Synopsis

**Protocol Title:** A Multicenter, Phase 1, Open-label, Dose-escalation and Expansion Study of AMG 340, a Bispecific Antibody Targeting PSMA in Subjects with Metastatic Castrate-resistant Prostate Carcinoma (mCRPC)

**Short Protocol Title:** Open-label, Dose-escalation, and Expansion Study of AMG 340 in Subjects with Metastatic Castrate-resistant Prostate Carcinoma

**Study Phase:** 1

**Indication:** Metastatic Castrate-resistant Prostate Carcinoma (mCRPC)

### Study Rationale

To evaluate the safety, pharmacokinetic/pharmacodynamic (PK/PD) properties, and clinical activity of the T-cell-engaging bispecific antibodies (T-BsAb) AMG 340 in subjects with metastatic castrate-resistant prostate carcinoma (mCRPC), this study will enroll subjects with progressive mCRPC that have been exposed to 2 or more lines of therapy. In order to be eligible for this study subjects should have previously been exposed to, intolerant of, ineligible for, or declined therapy with both a novel anti-androgen (eg, abiraterone, enzalutamide) and a taxane (eg, docetaxel).

Single-subject cohorts will initially receive AMG 340 once every 3 weeks (Q3W) beginning at a dose of █ mg (based on minimum anticipated biological effect level [MABEL]); once toxicity or activity emerges, subjects will be enrolled based on Bayesian optimal interval (BOIN) design. The objective of this study is to evaluate the safety of AMG 340 as monotherapy, find the maximum tolerated dose (MTD)/recommended phase 2 dose (RP2D) of AMG 340, and to establish the PK and PD characteristics of AMG 340. A Q3W dosing frequency was selected for initial dosing in Part A to allow adequate time for detection of toxicity between doses, and to limit drug accumulation.

Therapeutic options for advanced mCRPC are limited. Despite the success of chemotherapy, second generation non-steroidal anti-androgens, and androgen receptor blockers, patients that progress after treatment with these therapies have few therapeutic options. Therefore, patients that have progressive mCRPC and that have been exposed to 2 or more lines of therapy are proposed as eligible subjects for this study. Subjects should have previously been exposed to, intolerant of, ineligible for, or declined therapy with both a novel anti-androgen (eg, abiraterone, enzalutamide) and a taxane (eg, docetaxel).

## Objective(s) and Endpoint(s)

Objectives	Endpoints
Primary	

Evaluate the safety and tolerability of AMG 340 when administered as monotherapy.

	

Treatment-emergent adverse events

Treatment-related adverse events

Changes in vital signs and clinical laboratory tests

Determine the maximum tolerated dose (MTD) or recommended phase 2 dose (RP2D) for AMG 340 when administered as monotherapy.

	

Dose-limiting toxicities (DLTs)

Evaluate the pharmacokinetics (PK) of AMG 340 when administered as monotherapy.

	

PK parameters of AMG 340 including, but not limited to:

<math>C_{max}</math>

Time to <math>C_{max}</math> (<math>T_{max}</math>)

Area under the concentration-time curve within a dosing interval (<math>AUC_{0-t}</math>)

Secondary	

Evaluate the clinical activity of AMG 340 when administered as monotherapy.

	

Objective response (OR) per RECIST 1.1

Overall survival (OS)

Progression-free survival (PFS) (radiographic and PSA)

6-month landmark radiographic PFS

PSA response (30%, 50%, 70% and 90%)

Time to progression (radiographic and PSA)

Duration of response (DOR) per RECIST 1.1

PSA DOR based on PSA50

Time to symptomatic skeletal events (SSE)

## Overall Design

This is a phase 1 open-label, dose-escalation and expansion study evaluating the safety, PK, PD, and clinical activity of AMG 340 in subjects with progressive mCRPC who have

received at least 2 or more prior lines of systemic therapy ('Line/regimen of therapy' is defined as a course of therapy [at least 1 cycle uninterrupted by progressive disease, cycle disruption due to toxicity or intolerance is acceptable]). To be eligible for enrollment in this study, subjects should have previously been exposed to, intolerant of, ineligible for, or declined therapy with both a novel anti-androgen (eg, abiraterone, enzalutamide) and a taxane (eg, docetaxel).

The study will consist of 2 parts: a monotherapy dose escalation (Part A; Section 4.1.1) and a monotherapy dose expansion (Part B, Sections 4.1.2).

### **Number of Subjects**

The total number of subjects enrolled in both parts of the study is anticipated to be approximately 100 subjects (up to 60 subjects in Part A [monotherapy dose escalation] and up to 40 subjects in Part B [monotherapy dose expansion]) at sites in the US with a potential expansion to sites in Europe and the Asia-Pacific (APAC) region.

### **Summary of Subject Eligibility Criteria**

Adult male subjects with progressive mCRPC who have received 2 or more prior lines of systemic therapy approved for the treatment of mCRPC will be enrolled. Subjects should have previously been exposed to, intolerant of, ineligible for, or declined therapy with both a novel anti-androgen (eg, abiraterone, enzalutamide) and a taxane (eg, docetaxel).

For a full list of eligibility criteria, please refer to Section 5.1 and Section 5.2.

### **Treatments**

AMG 340 will initially be administered as an IV infusion Q3W, where 1 cycle of treatment will be 21 days. The starting dose of AMG 340 will be █ mg administered as an IV infusion (Q3W) in Part A and escalate to a projected maximum of █ mg in subsequent cohorts. In Part B, all subjects will receive AMG 340 at the MTD and/or RP2D. The dose(s) selected for evaluation in Part B may be a dose at or below the MTD defined in Part A or the RP2D. Dosing frequency for Part B will be chosen by the sponsor based on safety, tolerability, PK/PD, and clinical activity data collected from Part A, in consultation with the study investigators.

### **Statistical Considerations**

Descriptive statistics will be provided for selected demographics, safety data by dose, dose schedule, and time as appropriate. Descriptive statistics on continuous data will

include means, medians, standard deviations, and ranges, while categorical data will be summarized using frequency counts and percentages. Graphical summaries of the data may also be presented.

The proportion of subjects with an OR per RECIST 1.1 along with the corresponding exact 95% CI will be calculated using the Clopper-Pearson method (Clopper and Pearson, 1934); similarly, the proportion of subjects, 95% CI will be tabulated for PSA response. Kaplan-Meier quartiles, rates and curves will be used to summarize OS, rPFS, 6-month landmark rPFS, PSA PFS, time to progression (radiographic and PSA), time to symptomatic skeletal events (SSE), and DOR.

Unless otherwise specified, statistical analyses on safety endpoints will be done using subjects from the Safety Analysis Set, which includes subjects that are enrolled and received AMG 340. The analysis of DLTs will be conducted on the DLT Analysis Set. Subject incidence of DLT will be tabulated by planned dose level. The statistical analysis methods for other safety endpoints are described in Sections [9.4.2.3.2](#) through [9.4.2.3.6](#).

[figure not shown]
For a full description of statistical analysis methods, please refer to Section [9](#).

### **Statistical Hypotheses**

In Part A, a safe and tolerable dose of AMG 340 will have evidence of anti-tumor activity in subjects with mCRPC as measured by objective response rate (ORR). In Part B, AMG 340 will improve ORR in subjects with mCRPC to 20% compared with the reference ORR of 5%.

[figure not shown]
**Sponsor Name:** Amgen, Inc.

## 1.2 Study Schema

mCRPC = metastatic castrate-resistant prostate carcinoma; MTD = maximum tolerated dose; RP2D = recommended phase 2 dose

**Figure 1-2. Part A: Monotherapy Dose Escalation**

Note: The approximate number of subjects is based on lack of DATs in any cohort. The actual numbers of subjects will depend on safety and other findings.  
BOIN = Bayesian Optimal Interval; DAT = drug-associated toxicity; DLT = dose limiting toxicity; MTD = maximum tolerated dose; RP2D = recommended phase 2 dose.

## 1.3 Schedule of Activities (SoA)

Table 1-1. Schedule of Activities

Study Activity	Screening	C1 Treatment Period DLT Window (Days 1-21)										Treatment Period (3-week cycles)								UNS Visit a	EOT b	SFU n	Survival FU/LTFU o				
		W1					W2 d			W3		C2		C3			C4 & C5		C6		C7+						
		D1	D2	D3	D5	D6	D7	D8	D9	D10	D15	D1	D15	D1	D8	D15	D1	D1	D2	D15	D1						
Study Day	Day -28 to Day -1																					Within 30d after last dose	90d after last dose	Every 6 months			
Window				±1h	±1h	±1d	±1h	±1h	±1d	±1h	±1h	±1d	±1d	±1d	±1d	±1d	±1d	±1d	±1d	±1d							
Informed Consent	X																					+7d	±7d				
Incl/Excl Criteria	X	X																									
Inpatient Stay c		X	X	X	X c	X c	X c	X c	X c	X c																	
Demographics, Medical & Cancer History, Height	X																										
Complete Physical Exam	X																					X	X				
Symptom-directed Physical Exam		X	X	X	X	X i	X i	X	X k	X k	X	X	X	X	X	X	X	X	X	X	X	X	X				
Weight	X	X																									
Vital Signs d	X	X	X	X	X	X i	X i	X	X k	X k	X	X	X	X	X	X	X	X	X	X	X	X	X	X			
ECHO	X																										
12-Lead ECG	X																										
ECOG Performance Status	X	X																				X	X	X	X		
Clinical Chemistry and Hematology e	X	X	X	X	X	X i	X i	X	X k	X k	X	X	X	X	X	X	X	X	X	X	X	X	X	X			
Coagulation Panel e	X																										
Urinalysis	X																										
Viral Screen	X																										
Testosterone	X																										
AMG 340 administration f		X		X		X j						X	X	X	X	X	X	X	X	X	X						
Anti-AMG 340 antibody e																											

Refer to

Study Activity	Screening	C1 Treatment Period DLT Window (Days 1-21)										Treatment Period (3-week cycles)							UNS Visit a	EOT b	SFU n	Survival FU/LTFU o			
												C2			C3			C4 & C5							
		W1			W2 d			W3			W1	W3	W1	W2	W3	W1	W1	W3	W1	Within 30d after last dose	90d after last dose	Every 6 months			
Study Day	Day -28 to Day -1	D1	D2	D3	D5	D6	D7	D8	D9	D10	D15	D1	D15	D1	D8	D15	D1	D1	D2	D15	D1	UNS Visit a	EOT b	SFU n	Survival FU/LTFU o
Window		±1h	±1h	±1d	±1h	±1h	±1h	±1d	±1h	±1h	±1d	±1d	±1d	±1d	±1d	±1d	±1d	±1d	±1d	±1d	±1d	+7d	±7d		
Disease Assessments e, h		Refer to Table 1-3																							
Adverse event collection i	X	Recorded from the time of consent through SFU n																					X		
Serious adverse event collection m		Continuously throughout the study																							
Concomitant medications/therapy p		Recorded within 2 weeks from the first dose of study drug through SFU n																							
Survival																							X		

ADA = antidrug antibody; D = day; D/C = discharge; DLT = dose-limiting toxicity; ECG = electrocardiogram; ECHO = echocardiogram; ECOG = Eastern Cooperative Oncology Group; EOT = end-of-treatment; FU = follow-up; LTFU = long-term follow-up; PK = pharmacokinetic(s); SFU = safety follow-up; T1/2 = terminal half-life; UNS = unscheduled; W = week.

Note: Every effort should be made to keep the Schedule of Events on time for each subject.

a An unscheduled visit may occur at any time during the study. Study activities shown will be performed at the investigator's discretion.

b The EOT visit should occur within 30 days after the last dose of AMG 340. If an alternate therapy will be initiated during this period, the EOT visit should be conducted prior to the first dose of alternate therapy.

c Subjects will be admitted for 48 hours **after the infusion on C1D1 and, if implemented, after a second priming dose on C1D5**. If priming doses are **implemented**, subjects will also be admitted for 48 hours on C1D8 (note that a second priming dose may be implemented based on emerging data).

d Vital sign measurements include measurements of diastolic and systolic blood pressure, heart rate, respiratory rate, and temperature. On day 1 dosing, vital signs should be measured prior to study drug administration (up to 10 minutes before), 30 ± 10 minutes after initiation of study drug administration, at completion of study drug administration (±10 minutes), and 1 hour ± 10 minutes after completion of study drug administration; on C1D1 and on **C1D5 and C1D8**, if priming doses have been implemented, vital signs should also be measured 3, 6, and 9 hours ± 10 minutes after completion of study drug administration. Vital signs should be taken after 5 minutes of sitting or lying down.

f AMG 340 will be administered intravenously by continuous infusion pump over 120 minutes (± 10 minutes) unless otherwise noted in Section 6.1 of the protocol.

g CCI

h Samples will be collected for disease response as indicated in Table 1-3. Subjects off-treatment for reasons other than disease progression or withdrawal of consent should continue with disease response assessments as described in Table 1-3, until documented disease progression, initiation of subsequent anticancer therapy, or withdrawal (see Table 1-3).

i **C1D6 and C1D7 assessments will only be performed if a priming dose has been implemented on C1D5.**

j A dose will only be administered on C1D8 if a priming dose has been implemented.

k C1D9 and C1D10 assessments will only be performed if a priming dose has been implemented on C1D8.

l All adverse events observed by the investigator or reported by the subject that occur from the time of consent through the safety follow-up visit 90 (+ 7) days after the last dose of study drug should be reported. For subjects that start a new line of therapy before the 90 (+ 7) day follow-up visit, all adverse events should be collected and reported through 30 days post last dose of investigational product/protocol-required therapies or until the subject begins a new line of therapy, whichever occurs later (please refer to Section 8.1.3).

m All serious adverse events observed by the investigator or reported by the subject that occur from the time of consent through the safety follow-up visit 90 (+ 7) days after the last dose of study drug should be reported. For subjects that start a new line of therapy before the 90 (+ 7) day follow-up visit, all serious adverse events should be collected and reported through 30 days post last dose of investigational product/protocol-required therapies or until the subject begins a new line of therapy, whichever occurs later (please refer to Section 8.1.3). During the survival (long-term) follow-up phase, serious adverse events (regardless of causality) that the investigator becomes aware of will be reported to Amgen. After end of study, serious adverse events suspected to be related to investigational product should be reported to Amgen. Please refer to Section 8.4.6.1.3.

n The SFU visit should occur approximately 90 (+ 7) days after the end of the last dose of AMG 340. If a new line of therapy is initiated during this period, the SFU visit should be conducted through 30 days post last dose of AMG 340 or until the subject begins a new line of therapy, whichever occurs later.

o Subjects will be followed for survival and/or the commencement of subsequent cancer therapy via clinic visits, telephone, or chart review call every 6 months from the last SFU visit for up to a maximum of 3 years.

p Concomitant medications/therapy should be recorded within 2 weeks from the first dose of investigational product through the SFU or 30 days after last day of the dosing interval of investigational product/protocol-required therapies, whichever is later.

CCI

Footnotes described on last page of table

CCI

Footnotes described on last page of table

**Product:** AMG 340 (formerly TNB-585)

[figure not shown]
**Protocol Number:** 20210249 (formerly TNB585.001)

**Date:** 07 December 2022

---

Page 21 of 160

CCI

**Product:** AMG 340 (formerly TNB-585)

**Protocol Number:** 20210249 (formerly TNB585.001)

**Date:** 07 December 2022

---

Page 22 of 160

CCI

Table 1-3. Schedule of Disease Response Assessments

	SCR	Treatment Period a,g	EOT	SFU	Survival FU/LTFU	Notes
MRI brain	X					All subjects must have MRI of the brain performed within 28 days prior to the first dose of AMG 340. All brain scans on protocol are required to be MRI unless MRI is contraindicated, then CT with contrast is acceptable. Subsequently, MRI brain can be performed at any time if clinically indicated per standard of care.
CT/MRI b , bone scan c,f , and tumor burden assessment	X	Week 1-24 Day 1 of every 3 rd cycle (at C3D1 then every 9 weeks after C3D1)  Week 25+ Day 1 of every 4 th cycle (= every 12 weeks)	X d	X d	X e	CR/PR require confirmation after at least 4 weeks. Bone PD requires confirmation after at least 6 weeks. For subjects who discontinue for any reason other than radiographic disease progression, follow-up scans should occur every 3 months until documentation of disease progression per PCWG3.
 F-FDG PET/CT f	X	Every 12 weeks	X d	X d		Dose-expansion phase
PSA	X	Day 1 of every cycle	X	X		Disease assessments will be performed centrally.

a  $\pm$  7 days. Timing is based on first dose of AMG 340 (cycle 1 day 1).  
b Responses (PR and CR) require confirmation by a repeat consecutive CT/MRI assessment no sooner than 4 weeks after the first detection of radiographical response.  
c Per PCWG3 recommendations, the first post-treatment bone scan (at C3D1) will be used as the baseline scan with which all future bone scans are compared. To confirm disease progression by bone scan, a second bone scan must be performed at least 6 weeks after the 2nd of the 2 lesions is noted ("2+2" rule set).  
d Radiologic imaging (CT/MRI) and bone scan scintigraphy are required at the EOT or SFU visit if the subject has not had these imaging assessments performed within 6 weeks of the visit. For PET/CT imaging [REDACTED] and F-FDG), every effort should be made to acquire PET/CT scans at the EOT or SFU visit, or prior to initiation of other therapy if the subject has not had PET/CT imaging performed within 8 weeks of the visit.  
e For subjects who discontinued treatment for any reason other than radiographic disease progression, every effort should be made to perform radiographic imaging (CT/MRI/bone scan) of the chest, abdomen, pelvis, and all other known sites of disease every 3 months until documentation of radiographic disease progression per PCWG3, clinical progression, biochemical progression, start of new anticancer therapy, or up to 3 years after the first dose of study treatment.  
f Blood samples or tumor biopsy must not be collected until at least 24 hours after a PET/CT scan, or at least 60 hours (or 2.5 days) following a bone scintigraphy scan.  
g Subjects off-treatment for reasons other than disease progression or withdrawal of consent should continue with disease response assessments every 12 weeks ( $\pm$  7 days) until documented disease progression, initiation of subsequent anticancer therapy, or withdrawal.

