### **8.3 Efficacy Assessments**

#### **8.3.1 Radiographic Assessments**

Radiographic assessments will be obtained as scheduled in Table 1-3 (Schedule of Disease Assessments) relative to cycle 1 day 1 ( $\pm 7$  days) irrespective of cycle duration including dose delays and treatment discontinuation.

Radiographic scans taken to confirm disease progression following prior anti-cancer therapy may be used for baseline tumor assessments, provided they were performed within 28 days of enrollment and using the same contrast and modality planned to be used for all subsequent assessments.

Standard radiological assessments per protocol should take place until clinically significant disease progression or deterioration, withdrawal of consent, or start of new anticancer therapy. For subjects with PD continuing on treatment beyond progression, imaging should be continued as per local standard of care and images submitted to central reader. Every assessment must include computed tomography (CT)/magnetic resonance imaging (MRI) of the chest, abdomen, and pelvis, all other known sites of disease, and MRI of the brain if a subject has signs or symptoms suggestive of CNS metastases. The CT/MRI can be obtained earlier if clinical deterioration necessitates an

earlier scan at the discretion of the managing physician. The same scanner, contrast, and modality used at screening should be used for all subsequent assessments.

In the dose expansion phase only [REDACTED] PET/CT will be performed at baseline to assess PSMA-positive tumor burden, and every 12 weeks for response assessment. To identify PSMA-negative disease burden, F-FDG PET/CT will also be performed at baseline, and every 12 weeks for response assessment. All imaging assessments have a ± 7-day window. The use of [REDACTED] PET/CT and F-FDG PET/CT (in some countries/regions for prostate cancer) is investigational.

Tumor burden assessments will be performed based on Response Evaluation Criteria in Solid Tumors (RECIST) 1.1 with PCWG3 modifications (see Appendix 12

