## 11.9 Appendix 9. Activity Measurements

**Table 11-4. Response Categories Based on Assessment of Target Lesions**

	Complete Response	Partial Response	Stable Disease	Progression of Disease
Measurable lesions	
 
Disappearance of all target lesions. Any pathological lymph nodes (whether target or non-target) must have reduction in short axis to < 10 mm.
 
	
 
≥ 30% decrease in the sum of diameters of target lesions, taking as reference the baseline sum diameters.
 
	
 
Neither sufficient shrinkage to qualify for PR nor sufficient increase to qualify for PD, taking as reference the smallest sum diameters while on study.
 
	
 
≥ 20% increase in the sum of diameters of target lesions, taking as reference the smallest sum on study (this includes the baseline sum if that is the smallest on study).
 
The sum of diameters of target lesions must also demonstrate an absolute increase of at least 5 mm.
 
The appearance of 1 or more new lesions.
 

Non-measurable lesions	
 
Disappearance of all lesions.
 
	Not applicable	Not applicable	
 
Unequivocal progression of non-measurable lesions.
 
The appearance of 1 or more new lesions.
 

Bone lesions	
 
Disappearance of all lesions.
 
	Not applicable	Not applicable	
 
At least 2 new lesions on first post-treatment scan, with at least 2 additional lesions on the next scan (2+2 rule). 
 
If at least 2 additional new lesions are seen on the next (confirmatory) scan, the date of progression is the date of the first post-treatment scan, when the first 2 new lesions were documented.
 
For scans after the first post-treatment scan, at least 2 new lesions relative to the first post-treatment scan confirmed on a subsequent scan.
 
 
 

PSA	Not applicable	Not applicable	Not applicable	An isolated PSA increase is not sufficient for PD per PCWG3

PCWG3 = Prostate Cancer Working Group 3; PD = progressive disease; PR = partial response; PSA = prostate-specific antigen.

Source: Eisenhower et al, 2009; Scher et al, 2016.

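### Table 1-3 and Section 8.3.1 give conflicting stop rules for off-treatment imaging, and stopping at PSA or clinical progression can censor rPFS informatively

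*Protocol*

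**What the plan says.** Five places in the protocol govern imaging after treatment stops.

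- **Table 1-3, Notes column of the CT/MRI and bone scan row.** For subjects who discontinued for any reason other than radiographic progression, "follow-up scans should occur every 3 months until documentation of disease progression per PCWG3".
- **Table 1-3, footnote e**, attached to the survival/long-term follow-up cell of that row and covering the same subjects. Scans run every 3 months to PCWG3 radiographic progression, but also end at "clinical progression, biochemical progression, start of new anticancer therapy", or 3 years from the first dose.
- **Table 1-3, footnote g.** Subjects off treatment for reasons other than disease progression or withdrawal of consent "should continue with disease response assessments every 12 weeks", and this runs "until documented disease progression, initiation of subsequent anticancer therapy, or withdrawal". Radiographic is not specified.
- **Table 1-1, footnote h.** The same end-points as footnote g.
- **Section 8.3.1.** Standard assessments continue "until clinically significant disease progression or deterioration, withdrawal of consent, or start of new anticancer therapy". PSA is not mentioned.

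Protocol Table 11-4 adds: "An isolated PSA increase is not sufficient for PD per PCWG3".

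SAP Section 5.1.2 makes radiographic progression or death the only rPFS events. Under SAP Appendix D, a subject with no progression, death or new therapy is censored at the last evaluable radiographic assessment. One who starts new therapy first is censored at the last such assessment before it. Death without new therapy is an rPFS event, but is censored at the last scan for time to radiographic progression. The SAP describes no sensitivity analysis for imaging that ends early.

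**The concern.** A site can comply with footnote e and breach the Notes column for the same subject, so length of radiographic follow-up may depend on which line a site reads.

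The two additional exits in footnote e are not neutral. Neither clinical nor PSA progression is an rPFS event, and by Table 11-4 a PSA rise alone is not progressive disease. A subject whose imaging ends for either reason is still at risk of the event but no longer observed for it. Kaplan-Meier then treats that subject as having the same future risk as those still being scanned. If worsening PSA or symptoms tend to precede radiographic progression, which is clinically plausible but not quantified in the documents, the censoring is informative and the curve sits too high. At stake are three listed secondary endpoints: rPFS, 6-month landmark rPFS and time to radiographic progression. Missed scans cannot be recovered at analysis.

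**Working it through.** **1. The stop rules side by side**

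| Place (Protocol) | Ends at clinical progression? | Ends at PSA progression? | Progression specified as radiographic? |
|---|---|---|---|
| Table 1-3, Notes column | No | No | By PCWG3 |
| Table 1-3, footnote e | Yes | Yes | Yes, as one of several exits |
| Table 1-3, footnote g | Unclear | Unclear | No |
| Table 1-1, footnote h | Unclear | Unclear | No |
| Section 8.3.1 | Yes | Not named | No |

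The first two rows contradict each other for the same subjects and the same scans.

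**2. One subject through the SAP.** Take a subject who stops treatment for PSA progression with no radiographic progression. Under the Notes column, scans continue until the event is seen. Under footnote e, the stop condition is already met, so after any EOT or SFU scan due under footnote d no further imaging is called for.
- Alive, no new therapy: censored at the last evaluable scan.
- Dies without new therapy: an rPFS event at death, usually later than the unobserved progression. For time to radiographic progression, censored at the last scan.
- Starts new therapy: censored at the last scan before it, whichever stop rule applied.

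The first two paths tend to lengthen the estimate. The third exists under every rule except, read literally, the Notes column, which names no new-therapy exit.

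Table 1-3 schedules PSA only through SFU. A biochemical stop during long-term follow-up therefore has no scheduled measurement behind it.

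**3. The plan's own figure.** Part B has N = 40, ORR 5% versus 20%, one-sided alpha 0.1, exact binomial. Requiring at least 5 responders gives alpha 0.048 and power 0.924, which reproduces the stated 92%. (Requiring 4 gives alpha 0.138, above 0.1.) The imaging stop rule does not enter this calculation.

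**4. Illustration of the mechanism.** The documents give no progression rates, so everything here is assumed. Let time to radiographic progression be exponential with median M weeks (months × 52/12), with scans at weeks 6, 15 and 24 as in Table 1-3. The probability of progressing in interval j is d_j = 1 − 0.5^(interval length/M). Suppose a share q of the subjects about to progress in each interval have imaging stopped first and are censored at the previous scan. Each Kaplan-Meier factor becomes 1 − (1−q)d_j/(1−q·d_j) = (1−d_j)/(1−q·d_j), so the reported value is the full-follow-up value divided by the product of (1−q·d_j).

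Example, median 4 months: M = 17.33 and d = 0.2133, 0.3023, 0.3023. Full follow-up is 0.7867 × 0.6977 × 0.6977 = 0.383. With q = 0.2 the divisor is 0.9573 × 0.9395² = 0.845, giving 0.383/0.845 = 0.453.

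| Median | Full follow-up | q = 10% | q = 20% | q = 40% |
|---|---|---|---|---|
| 3 months | 27.8% | 30.9% | 34.5% | 43.5% |
| 4 months | 38.3% | 41.6% | 45.3% | 54.2% |
| 6 months | 52.7% | 55.9% | 59.3% | 67.0% |

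A simulation of 200,000 subjects agrees to within 0.3 of a point. The excess at 6 months is about 3 points at q = 10% and 14 to 16 at q = 40%. This sits at the unfavourable end: every affected subject is on the verge of progression, and EOT/SFU scans, deaths and new therapy are left out.

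**5. How far those omissions matter.** A second set of assumptions links PSA and radiographic progression through a shared frailty (medians 3–4 and 5–6 months; treatment stop 4–6 months). Imaging under footnote e ends at the later of treatment stop and PSA progression. Approximate 6-month excess:
- no EOT/SFU scans, deaths or new therapy: 2 to 5 points;
- adding EOT and SFU scans: 2.5 points or less;
- adding deaths as well: up to about 4 points;
- adding new therapy a median of 2 months after the stop, under both rules: about one point or less, and sensitive to modelling detail.

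**The case against.** The strongest reply is that the inconsistency has little practical effect, and several parts of it stand.

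- **Footnote d.** CT/MRI and bone scan are required at EOT or SFU if none was done within 6 weeks, with no PSA or clinical exit, and SFU is about 90 days after the last dose. Footnote e applies only to the follow-up cell after that. This shortens the unobserved period.
- **New therapy.** It ends imaging under footnotes e, g and h and Section 8.3.1, and the SAP censors there. Subjects who move quickly to another treatment are lost to rPFS with or without the clinical and PSA exits.
- **Shorthand.** The Notes column omits new therapy and the 3-year limit, so it could be read as a summary of footnote e. That is a possible reading, but a site cannot tell it from the text, and the Notes column names no PSA or clinical exit.
- **Soft wording.** Footnote e asks only for every effort. That affects how firmly scans are required, not which event ends them.
- **Precision.** With 40 subjects and 6-month rPFS near 55%, the 95% half-width is about 1.96 × √(0.55 × 0.45/40) = 0.154. A bias of a few points is small against that.

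A reader might also infer that footnote g already requires these scans to radiographic progression, so that aligning everything to it would suffice. The text does not support this. It excludes subjects who stopped for disease progression and ends at disease progression, and neither phrase is limited to radiographic findings. A subject who stopped for PSA progression can be read as outside it.

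**Conclusion.** The stop rules conflict and need reconciling. The conflict between the Notes column and footnote e is on the page and rests on no assumption. The consequence, informative censoring that tends to overstate rPFS, 6-month landmark rPFS and time to radiographic progression, follows from the SAP rules if PSA or clinical worsening tends to precede radiographic progression.

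The size cannot be determined from the documents. It depends on how many subjects stop treatment without radiographic progression, how soon they start new therapy, how many die untreated, and what the EOT/SFU scans catch. The range from about one point or less to about 16 points at 6 months is illustrative only, and its upper end excludes EOT/SFU scans, deaths and new therapy.

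Two stronger readings are tempting. One is that rPFS will be overstated by a known amount, or that a large share of subjects will be censored early because of footnote e. The plan gives no rates to support either, and some of that censoring would occur at new therapy anyway. The other is that the trial's main inference is compromised. It is not: the affected endpoints are secondary and descriptive, and the only powered hypothesis, ORR in Part B, does not depend on this rule. The point merits correction because the fix is cheap and the scans are otherwise lost.

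**What to change.** Use one stop rule in Table 1-3 footnotes e and g, the Table 1-3 Notes column, Table 1-1 footnote h and Section 8.3.1. Off-treatment imaging should continue until radiographic progression per PCWG3, new anticancer therapy, withdrawal of consent, or the 3-year limit.

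- In footnote e, delete the clinical and biochemical progression exits.
- In footnotes g and h, specify radiographic progression, both in the condition for who is followed and in the end-point.
- In Section 8.3.1, replace clinically significant progression or deterioration with the same rule.
- In the Notes column, add the new-therapy, withdrawal and 3-year limits so that it matches.

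In the SAP, an rPFS sensitivity analysis counting clinical progression or new anticancer therapy as events would show how much the remaining censoring matters, since censoring at new therapy persists after the change.

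The cost is a few lines of amendment text and some additional scans relative to footnote e alone. The Notes column already calls for those scans. Sample size, power and treatment rules do not change.
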